**2) Objectives**

To demonstrate the safety, efficacy, and feasibility of teduglutide in patients with ECF; to evaluate quality of life in patients with ECF receiving teduglutide

**Hypothesis**

We hypothesize that administration of teduglutide to patients with ECF is safe, feasible, and effective in reducing fistula output by 20% and improving quality of life.

**Design**

Open label cross-over pilot study to determine safety and efficacy of teduglutide in patients with ECF. Our planned sample size is 10 subjects randomized and treated with at least 1-dose of study drug .

IRB Study Number: 20170189  
Version Date: June 16, 2021  
PI: [name]

NCT02889393

The primary efficacy end point will be decrease in fistula volume by 20% from baseline 3-day average, as measured by the patient.

The secondary efficacy end points will be cessation of fistula output altogether and health-related quality of life questionnaire score as assessed by the questionnaires (see below) at time points Study Visit 5, 10, and 11 (3 months after end-of-treatment).

Subjects that complete both arms of the study who have a favorable (but incomplete) response and are deemed to be reliable (both as determined by the principal investigator) will be offered an open-label extension during which they will continue to receive teduglutide for up to another 12 months or permanent fistula closure, whichever occurs first.

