#### **4) Entry Criteria**

##### **Inclusion criteria**

- a) Age >18
- b) Enterocutaneous fistula (ECF) that could be secondary to volvulus, injury, prior trauma or surgery, or vascular ischemia

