### **Enrollment within 2 months of signing consent**

Inclusion/Exclusion criteria

Vital signs measurements

Nutritional assessment

3-day average fistula output

Complete questionnaires (see additional documents):

1. ASCQ-Me Short Form v2.0 - Social Functioning Impact
2. ASCQ-Me v2.0 - Sleep Impact Short Form

IRB Study Number: 20170189  
Version Date: June 16, 2021  
PI: [name]

NCT02889393

3. Global Health Scale v1.2
4. PROMIS Scale v1.0 - GI Belly Pain
5. PROMIS Scale v1.0 - GI Diarrhea
6. PROMIS Scale v1.0 - GI Nausea and Vomiting
7. PROMIS SF v2.0 - Ability to Participate

Teaching of self-administration of medication

After study enrollment, the subject will be randomly assigned (by a computerized method, using the site 'www.sealedenvelope.com') to begin teduglutide treatment immediately or to continue standard of care (SOC) treatment. The randomization will be performed by a member of the study that is not involved in the informed consent process, and will be enclosed in sequentially numbered opaque envelopes. The envelopes will be given to the PI prior to the enrollment visit. At study visit 5 (day 56), the subject will then cross-over to the opposite treatment assignment. The half-life of teduglutide is 2-3 hours. During the period the subjects are on the "SOC only" treatment arm, the subjects will be given the option to replace some Study visits with Telephone Calls for their convenience. If study visits overlap due to the time window, either visit may be skipped or completed on the same day. Please see information below, and the Study schema.

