**Study Visit 5, Cross-over, (Day 56) (+/- 1 week)**

Collect physical examination  
Collect Vital Signs measurements  
Chemistry Panel (sodium, potassium, chloride, bicarbonate, blood urea nitrogen, creatinine glucose)  
Liver Function tests (total bilirubin, direct bilirubin, alkalkine phosphatase, alanine aminotransferase, aspartate aminotransferase, lipase, amylase)

IRB Study Number: 20170189  
Version Date: June 16, 2021  
PI: [name]

NCT02889393

Plasma PK (Pharmacokinetics)

- Processed according to separate “Sample Processing Procedure”

Serum pregnancy test

Monitor severe adverse events (SAE) and adverse events (AE)

Collect Concomitant medication review

Collect Nutritional Assessment

3-day average fistula volume (3 days immediately preceding study visit)

Collect adjustment of medications and fluids if recorded

Fistula closure (y/n)

Complete Questionnaires (see additional documents)

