## **7) Biostatistical Analysis**

Because this is a pilot study enrolling only 10 subjects, no sample size or power calculation was performed. The primary endpoint (decrease in fistula volume by 20%) was chosen based on previous studies in a different population.

Continuous outcome variables that are normally distributed will be presented as mean  $\pm$  Standard Deviation (SD) while continuous outcome variables that are not normally distributed will be presented as median and interquartile range (IQR). In calculating the difference in fistula volume between baseline and final measures, a two-sample t-test for independent samples will be used. A p value of <0.05 will be considered significant.

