### **10) Potential Benefits to Subjects**

Based on the encouraging results in studies of teduglutide for patients with short bowel syndrome, we expect a clinically significant decrease in daily ECF volume of about 20% magnitude. This could convert high-output fistulas (>500 mL/day) to medium- (200-500 mL/day) or low-output fistulas (<200 mL/day), significantly simplifying fluid/electrolyte management, allow for liberation from parenteral nutrition, or even resolve low-output fistulas completely. It is reasonable to expect an improvement in quality of life.

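### The primary endpoint is a 20% decrease in fistula volume, but the only planned test is against zero change in mL, and no analysis of the 20% criterion is planned

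*Combined protocol and SAP*

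**What the plan says.** Three places set 20% as the efficacy target. The Hypothesis expects teduglutide to be "effective in reducing fistula output by 20% and improving quality of life". The Design section makes it the primary endpoint: "The primary efficacy end point will be decrease in fistula volume by 20% from baseline 3-day average, as measured by the patient". Section 7 repeats it: "The primary endpoint (decrease in fistula volume by 20%) was chosen based on previous studies in a different population".

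Section 7 then gives the whole inferential plan: "In calculating the difference in fistula volume between baseline and final measures, a two-sample t-test for independent samples will be used". The significance level is 0.05; sidedness and margin are not stated. Descriptive statistics are mean and SD, or median and IQR, for continuous outcomes. The section also says that no sample size or power calculation was done for the 10 subjects.

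Section 10 (Potential Benefits to Subjects) words the figure differently: "we expect a clinically significant decrease in daily ECF volume of about 20% magnitude".

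Fistula volume is listed in section 6 as a continuous data field, with a yes/no flag for output above 500 mL/day. There is no field for reaching a 20% decrease.

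**The concern.** A t-test with no stated margin asks whether mean volume differs from zero change. The endpoint asks whether volume fell by 20%. A p-value below 0.05 does not show that the endpoint was met, and one above 0.05 does not show that it was missed. Nothing else in the plan fills the gap.

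The endpoint is also open in two respects that matter once someone tries to analyse it.

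- **Per patient or average.** The Design wording can be read as a response in each patient. Section 10 reads more like an average fall.
- **Which measurements.** A 3-day average is collected both at screening and at enrollment ("3-day average fistula output"), and neither is named as baseline. The final value could be Day 56, Day 112 or the long-term follow-up visit.

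In an open-label trial with patient-measured output, these choices are best fixed before the data are seen.

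**Working it through.** **Inputs from the documents:** n=10; threshold 20%; alpha 0.05 (taken as two-sided); unpaired t-test on volume. **Assumed:** all volumes below, evenly spaced across the stated range, because the documents give no SD. The plan has no figure of its own to reproduce.

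**Formula for the planned test:** t = (mean baseline − mean final) / √[(SD_b² + SD_f²)/10], on 18 degrees of freedom.

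**1. Significant, but nobody reaches 20%.** Baselines 420-580 mL/day, every patient falls 12%.
- Means 500 and 440; SDs 53.8 and 47.4.
- t = 60 / 22.67 = 2.65, p = 0.016. Patients at 20% or more: 0/10.
- This needs a narrow spread (SD/mean = 0.11). With baselines 300-700 mL/day and the same 12% fall, SDs are 134.6 and 118.4, t = 60 / 56.68 = 1.06, p = 0.30.

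**2. Not significant, but everybody reaches 20%.** Baselines 300-1200 mL/day, every patient falls 25%.
- Means 750 and 562.5; SDs 302.8 and 227.1.
- t = 187.5 / 119.68 = 1.57, p = 0.13. Patients at 20% or more: 10/10.
- Treating paired values as independent contributes to this result.

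**3. Would pairing alone cure it?** No. A paired test would still have a null of zero. On the data of step 1 a paired test, which is not the planned one, gives p = 3×10⁻¹⁰, still with 0/10 reaching 20%.

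**4. Does the reading of 20% matter?** The 95% CI for a mean percent change is mean ± 2.262 × SD/√10.

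| Assumed changes | Mean | 95% CI of mean | Patients at ≥20% decrease |
|---|---|---|---|
| 3 at −60%, 7 at −3% | −20.1% | −39.8 to −0.4 | 3/10 |
| 7 at −25%, 3 at +10% | −14.5% | −26.6 to −2.4 | 7/10 |

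The average points towards 20% in the first set and the responder count in the second. Both intervals include −20%.

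**5. How precise would an analysis of the 20% be?**
- Mean percent change: 2.262 × 20/√10 = 14.3 points and 2.262 × 40/√10 = 28.6 points, for assumed SDs of 20 and 40 points. For the interval to exclude falls smaller than 20%, the observed mean fall must be about 34 (20 + 14.3) to 49 (20 + 28.6) points.
- Responders: 6/10 has an exact 95% CI of 26% to 88%.

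**The case against.** The strongest reply is that 20% is the expected effect, not a threshold. Section 10 says as much, and testing against zero is ordinary practice when a target effect has been named. This softens the point but does not remove it: the Design section and section 7 both call the 20% decrease the endpoint itself, and no rule links the test to it.

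A reader might infer that the test has nothing to do with the endpoint. That goes too far. It uses the endpoint's own variable, and if means are reported at baseline and at the final measurement, the fall in mean volume follows by division. What is missing is the within-patient percent change, its uncertainty and the number of patients reaching 20%.

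It is also fair that a significant result well short of 20% is unlikely with the test as planned. The inclusion criteria define the fistula by cause ("that could be secondary to volvulus, injury, prior trauma or surgery, or vascular ischemia") and set no minimum output, so baselines may vary widely, and step 1 shows significance disappearing once they do.

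Finally, this is a 10-subject pilot and any interval will be wide. That excuses the absence of a power calculation. It does not excuse having no analysis of the stated primary endpoint.

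**Conclusion.** The concern holds in this limited form: the plan tests for zero change in mL and nowhere analyses the 20% decrease that it names as its primary endpoint. The structural point rests on the text alone. The p-values in steps 1 and 2 rest on assumed volumes and only show that significance and the 20% criterion can separate in either direction.

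Two stronger readings are not supported. One is that the plan will lead to a false claim of success or failure: it sets no success rule, so the harm is an unanswered primary question. The other is that the per-patient and average readings give opposite answers: they can point different ways, but with no success rule and with both mean intervals including −20%, neither example is decisive.

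This should be corrected. The stakes are those of a small pilot.

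**What to change.** **Design section.** State whether the 20% applies to each patient or to the average. Define baseline as the enrollment 3-day average, and final as the 3-day averages at Day 56 and Day 112, the end of each period.

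**Section 7.** Replace the t-test on mL with:
- within-patient percent change in each treatment period, with a 95% CI read against 20%;
- the median percent change;
- the number of patients with a decrease of at least 20% in each period, with exact 95% CIs;
- all of these tabulated by treatment and sequence.

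**Cost.** Wording in two sections; the 3-day averages are already collected. There are three downsides.
- Precision is low (step 5), so the result stays mainly descriptive.
- Mean percent change is fragile when baselines are low: nine patients at −30% and one at +150% average −12% (±41 points), while the median is −30%. This is why the median is included.
- With the enrollment baseline used in both periods, standard of care after teduglutide carries any persisting effect, and teduglutide after standard of care carries eight weeks of drift. The contrast between teduglutide and standard of care is a separate matter that this change does not settle.

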**Study Visit 10, End of Treatment (EOT), (Day 112) (+/- 1 week)**

Collect physical examination  
Collect Vital Signs measurements  
Chemistry Panel (sodium, potassium, chloride, bicarbonate, blood urea nitrogen, creatinine glucose)  
Liver Function tests (total bilirubin, direct bilirubin, alkalkine phosphatase, alanine aminotransferase, aspartate aminotransferase, lipase, amylase)  
Plasma PK (Pharmacokinetics)

- Processed according to separate "Sample Processing Procedure"

Serum pregnancy test  
Monitor severe adverse events (SAE) and adverse events (AE)  
Collect Concomitant medication review  
Collect Nutritional Assessment  
3-day average fistula volume (3 days immediately preceding study visit)  
Collect adjustment of medications and fluids if recorded  
Fistula closure (y/n)  
Complete Questionnaires (see additional documents)

IRB Study Number: 20170189  
Version Date: June 16, 2021  
PI: [name]

NCT02889393

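### The primary endpoint compares baseline with final fistula output without tying either reading to the patient's own teduglutide period

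*Combined protocol and SAP*

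**What the plan says.** The Design section defines the endpoint: "The primary efficacy end point will be decrease in fistula volume by 20% from baseline 3-day average, as measured by the patient". It gives no assessment visit, although the same section ties the questionnaire scores to Visits 5, 10 and 11. Section 7 (Biostatistical Analysis) says: "In calculating the difference in fistula volume between baseline and final measures, a two-sample t-test for independent samples will be used". It does not say which visits supply the two values, or whether they depend on period or sequence.

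Patients are randomised to start teduglutide at once or to continue SOC; no allocation ratio is given. Then: "At study visit 5 (day 56), the subject will then cross-over to the opposite treatment assignment". The drug administration section sets dosing at 8 weeks. The Day 112 visit heading begins "Study Visit 10, End of Treatment (EOT), (Day 112) (+/- 1 week" and applies to both sequences; Appendix E uses the same label.

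A 3-day average output is recorded at Screening, Enrollment, Visit 5 (Day 56), Visit 10 (Day 112), Visit 11 and the contacts in between. On size, section 7 says "Because this is a pilot study enrolling only 10 subjects, no sample size or power calculation was performed".

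**The concern.** The endpoint is meant to show what teduglutide does to fistula output. That needs one reading just before the first dose and one at the end of dosing. Dosing occupies a different half of the study in each sequence, so those two points are different visits in the two sequences, and the plan does not say so.

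The only 3-day averages before randomisation are at Screening and Enrollment, and Day 112 is the only visit called end of treatment. Enrollment to Day 112 is therefore the pair an analyst would most naturally pick. On that choice, teduglutide-first patients contribute a final value taken long after the drug stopped, which dilutes the effect unless it persists. SOC-first patients contribute a change that includes 8 weeks of SOC and natural course before any drug.

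The study is open label with 10 patients and patient-measured output. Leaving the visits open also means that the same data can give different primary results, depending on which visit is later called final. A different statistical test would not cure this.

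**Working it through.** The plan has no power or sample-size figure to reproduce. The check is timeline arithmetic, then an illustration.

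**Inputs from the protocol.** Enrollment is taken as Day 0, cross-over is at Day 56, Visit 10 is at Day 112, and dosing lasts 8 × 7 = 56 days. Teduglutide-first patients are on drug from Day 0 to 56, and SOC-first patients from Day 56 to 112. Visit 11 is 3 months after Day 112; taking 90 days, that is Day 202.

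**Step 1: alignment of common visit pairs**

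| Pair used for everyone | Teduglutide-first | SOC-first |
|---|---|---|
| Enrollment to Day 112 | 56 of 112 days on drug; final reading 112 − 56 = 56 days after last dose | 56 of 112 days on drug; baseline 56 − 0 = 56 days before first dose |
| Enrollment to Day 56 | 56 of 56 days on drug | 0 of 56 |
| Day 56 to Day 112 | 0 of 56 | 56 of 56 |
| Enrollment to Visit 11 | final reading 202 − 56 = 146 days after last dose | baseline 56 days before first dose; final reading 202 − 112 = 90 days after last dose |

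The general reason is that first doses fall at Day 0 in one sequence and Day 56 in the other. No single visit can be the pre-dose reading for both, so every common pair is misaligned for at least one sequence.

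**Step 2: dilution on the Enrollment to Day 112 reading.** Assumptions, none given in the documents: a true on-drug fall of 20%; a share c of it remaining 8 weeks after stopping; a natural fall t in each 8 weeks; effects multiplicative; 5 patients per sequence.

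- Teduglutide-first: 1 − (1 − t)²(1 − 0.20c)
- SOC-first: 1 − (1 − t)²(1 − 0.20)

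| t | c | Teduglutide-first | SOC-first | Mean |
|---|---|---|---|---|
| 0 | 0 | 0% | 20% | 10% |
| 0 | 0.5 | 10% | 20% | 15% |
| 0 | 1 | 20% | 20% | 20% |
| 10% | 0 | 19% | 35.2% | 27.1% |

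With t = 0 and c = 0, splits from 7:3 to 3:7 (teduglutide-first to SOC-first) give means from 3 × 20%/10 = 6% to 7 × 20%/10 = 14%.

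**Step 3: sequence-specific readings.** Enrollment to Visit 5 (teduglutide-first) and Visit 5 to Visit 10 (SOC-first) give 56 of 56 days on drug in both. The measured fall is 1 − (1 − t)(0.80): 20% at t = 0, whatever the value of c, and 28% at t = 10%. Alignment is restored, but natural decline remains in the result.

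**Step 4: end-of-teduglutide against end-of-SOC, within patient.** With c = 0, the ratio is 0.80/(1 − t) in teduglutide-first and 0.80(1 − t) in SOC-first. At t = 10% these are 0.889 and 0.720; the geometric mean is √(0.889 × 0.720) = 0.80, so weighting the sequences equally recovers the 20%. An SOC change measured from Visit 5 would not serve. In teduglutide-first patients with t = 0 and c = 0, output goes from 80 to 100 units, a 20/80 = 25% rise that is rebound after stopping drug, not an SOC effect.

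**The case against.** The documents nowhere fix the final reading at Day 112; neither value is defined. Some text fits treatment-based timing: the drug administration section has teduglutide start once baseline data are in hand, and section 8 places blood draws by weeks of treatment. A reader might infer that the plan prescribes a wrong pair of visits, that the readings fail to enclose the drug period in both sequences, or that the endpoint is measured wholly off drug. The documents support none of these. Enrollment to Day 112 contains all 56 drug days in both sequences, each sequence is misaligned at one end only, and the SOC-first Day 112 value is on drug. Nor are usable data lacking, since readings at both ends of dosing are scheduled for every patient.

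The size also depends on assumptions. If the effect persists fully and there is no natural change, the mean is 20% and nothing is lost. The two biases can also offset. With a single 10% natural fall in the first 8 weeks that then holds, and full reversal, Enrollment to Day 112 gives 10% and 1 − 0.90 × 0.80 = 28%, mean 19%. The sequence-specific readings give 28% and 20%, mean 24%. The first mean is closer to the true 20%, but only because two errors cancel. The example does show that aligned readings alone do not remove natural decline.

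Finally, this is a pilot without a power claim, and a common pre-randomisation baseline is legitimate in a cross-over if end-of-period values are compared within patient. Section 7 does not specify that comparison. These points limit how strongly the concern can be put; they do not supply the missing definition.

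**Conclusion.** The concern holds in conditional form. The primary endpoint and its analysis are not tied to the teduglutide period. On the most natural reading, the final value is about 8 weeks off drug in teduglutide-first patients and the baseline is about 8 weeks before drug in SOC-first patients. No other common pair of visits aligns both sequences. The timeline part needs only the visit schedule, with the visit windows (± 1 week at Days 56 and 112) making the day counts approximate.

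The measured average of 10% to 20% against a true 20% is illustrative. It rests on an assumed 5:5 split, no natural change and persistence from none to full, and the documents give no figure for any of these. Natural decline acts in the other direction, raising the SOC-first change. The point should be settled before the primary analysis, because the baseline-to-final contrast as worded does not isolate the drug effect.

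**What to change.** In the Design section and section 7, define the readings by sequence:

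- **Pre-drug:** the last 3-day average before the first dose (Enrollment if teduglutide-first, Visit 5 if SOC-first).
- **On-drug:** the 3-day average at the end of dosing (Visit 5 if teduglutide-first, Visit 10 if SOC-first).

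Use this pair for the 20% responder endpoint. Because natural decline alone can still produce a 20% fall, also compare each patient's end-of-teduglutide reading with that patient's end-of-SOC reading (Visit 5 against Visit 10, accounting for period). Do not use an SOC change from Visit 5, for the rebound reason shown above. State one limitation: with no washout described, any effect persisting to Day 112 in teduglutide-first patients would shrink this comparison.

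Reserve the term end of treatment for each patient's own end of dosing. Visit 10 then needs a neutral label, such as end of period 2, in its heading and in Appendix E. Visit 11 is timed from end of treatment, so its description must refer to Visit 10 if its timing is to stay as scheduled.

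The cost is wording only. All the readings are already collected, and no visits or patients are added.

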**Study Visit 1 or Telephone Call as applicable (Day 7) (+/- 3 days)**

Collect physical examination if during visit

Collect Vital Signs measurements if during visit

Monitor severe adverse events (SAE) and adverse events (AE)

Collect concomitant medication review

Collect Nutritional Assessment

3-day average fistula volume (3 days immediately preceding study visit) from the Diaries

Collect adjustment of medications and fluids if recorded

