#### **Data Fields**

Age

BMI

Gender

Charlson Comorbidity Index

Questionnaires (see additional documents)

Cause of major intestinal resection: trauma, emergency operation, elective operation, inflammatory bowel disease, other

Location of fistula: stomach, duodenum, jejunum, ileum, colon

Days since last operation

Days since fistula diagnosis

Type of nutrition: per os (PO), enteral nutrition (EN), parenteral nutrition (PN), PO + EN, PO + TPN, EN + PN, PO +EN + PN

IRB Study Number: 20170189  
Version Date: June 16, 2021  
PI: [name]

NCT02889393

Concomitant medications: antidiarrheals, antisecretory agents  
3-day average fistula volume (continuous variable)  
Output of fistula >500 mL/day (Y/N)

Because of the expected increase in luminal absorption, subjects will be closely monitored for increased oral medication absorption, particularly opioids and sedating medications. Subjects will be assessed for pinpoint pupils and lethargy. If clinical evidence of increased oral medical absorption is discovered, the doses will be accordingly decreased. If clinical evidence of fluid overload is discovered (such as breathlessness, subjective dyspnea, new-onset pitting peripheral edema, change in body weight, jugular venous distention, and rales on lung auscultation), then EN and PN prescription will be decreased accordingly.

Additionally, subjects will be monitored for clinical evidence of volume depletion. Clinical signs suggestive of volume depletion include dry mucus membranes, poor skin turgor, decreased urine output, or rapid body weight loss.

Fluid and volume status will be assessed according to the usual clinical signs and symptoms: breathlessness, subjective dyspnea, new-onset pitting edema, change in body weight, and rales on lung auscultation. This will be assessed both in person at the time of study visit as well as by self report from the subject during phone calls.

Criteria for discontinuation of teduglutide in patients who experience fluid overload include: decrease in room-air oxygen saturation > 5% from baseline, significant worsening of peripheral edema resulting in functional limitation, severe dyspnea resulting in functional limitation, and hospitalization for congestive heart failure.

Data will be de-identified and stored on password-protected network accessible only to research staff. Data will be retained for at least six years following conclusion of the study on this network.

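### The primary comparison sets a baseline 3-day average against an undefined final measure and leaves the repeat 3-day averages already collected unused; how much this costs depends on what the 20% means and on within-patient variability

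*Combined protocol and SAP*

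**What the plan says.** The Design section defines the primary efficacy endpoint as a "decrease in fistula volume by 20% from baseline 3-day average, as measured by the patient". It names no assessment day and does not say whether each patient is to be classified or a mean change is meant.

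Section 7 gives the only planned test: "In calculating the difference in fistula volume between baseline and final measures, a two-sample t-test for independent samples will be used". Neither the baseline nor the final measure is defined there, and no analysis of responder proportions is described. The same section states "Because this is a pilot study enrolling only 10 subjects, no sample size or power calculation was performed".

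The visit schedule collects far more than two values per patient:
- Two pre-treatment 3-day averages, one at screening and one at enrollment. Enrollment may fall up to 2 months after consent.
- Eight averages in the first period (Days 7, 14, 21, 28, 35, 42, 49 and 56) and eight in the second (Days 63 to 112 at the same spacing), counting the telephone calls. The Day 7 entry, for example, reads "3-day average fistula volume (3 days immediately preceding study visit) from the Diaries".
- One more at Study Visit 11.

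Appendix E shows the same schedule. The documents do not say which pre-treatment average is the baseline or how the repeats are to be combined.

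**The concern.** A 3-day average of self-measured output carries day-to-day variation. When one such average is divided by another, both errors enter the ratio, and a 20% fall can arise with no true change. The plan is for 10 patients, so each misclassified patient moves a responder rate by 10 percentage points, and two or three chance responders could be read as efficacy.

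If the 20% is instead an average effect, symmetric noise does not bias the comparison. It does make it less precise than the collected data allow.

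Under either reading, an unstated final window leaves the choice of window open until after the data are seen, in an open-label trial with a patient-measured outcome.

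**Working it through.** The plan gives no power figure or misclassification rate to reproduce.

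**Inputs from the documents.** Threshold 20% (Design); 10 patients (Design, section 7); two pre-treatment windows and eight windows per period (visit schedule, Appendix E).

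**Assumptions, not in the documents.** The within-patient CV of a 3-day average is 10%, 20% or 30%. Errors are roughly normal on the log scale with SD equal to the CV. Repeats on the same side (baseline or late) are either independent or correlated 0.5, and baseline errors are independent of late errors. For scale, a 3-day CV of 20% corresponds to a single-day CV of about 35% if days are independent (0.20 × √3), or about 24% if days within a window correlate 0.5 (0.20 / √(2/3)).

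**Formula.** For a patient with no true change, P(fall of at least 20%) = Φ( ln 0.8 / (CV × √V) ), with ln 0.8 = −0.223. V is the sum of the baseline and late variance factors. For the mean of n windows with correlation r, the factor is (1 + (n − 1)r)/n.

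**Variance factors.**
- One window against one: V = 1 + 1 = 2, √V = 1.414.
- Two against three, independent: V = 1/2 + 1/3 = 0.833, √V = 0.913.
- Two against three, r = 0.5: V = 0.750 + 0.667 = 1.417, √V = 1.190.

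**False-responder probability.**

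| CV of 3-day mean | 1 v 1 | 2 v 3, independent | 2 v 3, r = 0.5 |
|---|---|---|---|
| 10% | 5.7% | 0.7% | 3.0% |
| 20% | 21.5% | 11.1% | 17.4% |
| 30% | 29.9% | 20.8% | 26.6% |

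At CV 20%, for example: −0.223/(0.20 × 1.414) = −0.789, so Φ = 0.215.

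**In 10 patients, none truly changed.** One window against one gives an expected 0.6, 2.2 or 3.0 false responders. At CV 20% the chance of three or more is 37% (binomial, p = 0.215). It falls to 9% with averaging and independent errors (p = 0.111), or 25% at r = 0.5 (p = 0.174).

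**Precision of the change from baseline (log scale).** The SD falls by 1 − 0.913/1.414 = 35% (independent) or 1 − 1.190/1.414 = 16% (r = 0.5).

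**Limits of averaging.**
- *Late effect.* If a 33% fall (the short-bowel figure quoted in Background) appears only in the last of three windows, the period mean falls by 33%/3 = 11%, below the threshold.
- *Drift before enrollment.* If output at screening was 20% above its enrollment level, the averaged baseline is 10% too high. At CV 20% with independent errors, a patient unchanged since enrollment then crosses the threshold with probability Φ( ln(0.8 × 1.1)/(0.20 × 0.913) ) = 24%. Enrollment alone against three late windows gives Φ( −0.223/(0.20 × √(1 + 1/3)) ) = 17%.

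**The case against.** The strongest reply is that no responder rule is clearly set. The only planned test is on volume, the data field is listed as continuous, and the Potential Benefits section speaks of an expected decrease of roughly 20%, which reads as an average effect. On that reading there are no false responders to count. This stands, and it is why the probabilities above are conditional.

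A second reply is that a single final window is inferred. That also stands in part. The plan leaves the final measure undefined; it does not choose one window. With no combining rule, one window is the natural reading, and nothing in the plan excludes it.

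Third, the size rests on a CV that the documents do not give. At a 3-day CV of 10% the problem is small, about 0.6 false responders in 10.

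Fourth, the randomized standard-of-care period is the design's own guard, because unchanged patients would cross 20% there too. This is right, but section 7 compares baseline with final and names no comparison of teduglutide with standard of care.

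A reader might also infer that a 20% fall at any of the eight weekly windows would count, which would raise the rate sharply. No section proposes such a rule, so that figure does not describe this plan.

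**Conclusion.** The point holds as a gap in definition, at a cost that can be bounded but not fixed from the documents. The baseline and final measures are not defined, and repeat averages already in hand are unused. If the threshold is applied to individuals, about 6% to 30% of unchanged patients would cross it over an assumed 3-day CV of 10% to 30%. If the 20% is a mean change, the loss is one of precision only.

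Two stronger conclusions are not supported. One is that the plan would label many unchanged patients as responders: that needs both a per-patient rule and a CV toward the upper part of the assumed range. The other is that the repeat windows cure the problem. At CV 20% averaging takes 22% to 11% at best, and only to 17% if repeats correlate 0.5. It does not correct drift or spontaneous closure; the comparison with standard of care has to do that.

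**What to change.** Make these changes in the Design section and section 7 before the data are analysed:

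1. State whether 20% is a per-patient rule or a mean change.
2. Define each period's value as the mean of its last three collected 3-day averages, nominally Days 42, 49 and 56 and Days 98, 105 and 112. If one is skipped, use those available, since the Enrollment section allows overlapping visits to be skipped or merged.
3. Define baseline as the mean of the screening and enrollment averages. Add enrollment alone as a sensitivity analysis, because the two can be up to 2 months apart.
4. Compare teduglutide and standard-of-care period values within patient, as percent change from baseline or on another scale that admits zero output. A log ratio is undefined for a closed fistula and would lose the best outcomes.
5. Estimate the within-patient CV from the standard-of-care windows and report it beside any responder count.

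The cost is wording and analysis time; no visits, samples or patients are added. The main downside is that an effect seen only in the last week is diluted to about one third. Three late windows, rather than a longer run, are proposed to limit this.
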